1.1 Introduction

Gastroesophageal reflux disease(GERD) is a widely prevalent medical disorder in the United States with a spectrum of treatment options ranging from dietary modification, to various pharmacologic treatments, to an array of available surgical and endoscopic procedures. There is a well-described correlation between obesity and symptoms of GERD. The morbidly obese patients undergoing evaluation for bariatric surgery are to characterize any GERD-like symptoms as this will assist in directing surgical therapy. Generally, it is recommended that patients with severe GERD undergo Roux-en-Y gastric bypass(RYGB) rather than a sleeve gastrectomy (SG) as RYGB has proven to be the most effective surgical treatment for GERD in the morbidly obese patient. The number of bariatric procedures performed in the United States has increased significantly in the recent years. Out of all bariatric procedures SG is the most commonly performed in the United States, as it has proven to be a very safe procedure with excellent weight loss. However, the incidence of de novo GERD and the effect of SG on patients with preexisting GERD remain controversial. Although some authors report high incidence of de novo GERD and worsening of previous reflux symptoms, there is also data showing improvement of symptoms post SG. Management of GERD after SG poses an interesting challenge, as traditional invasive procedures likeNissen fundoplication are not available due to an altered gastric anatomy. The alternative is to perform a conversion to RYGB, which represents increased morbidity to patient and significant cost.

A large number of endoscopic procedures have been introduced in the past for the management of GERD as an alternative to the surgical anti-reflux procedures with various degrees of success. One of the few non-invasive methods for managing GERD that is still available on the market and widely used is Stretta. Stretta delivers Radio Frequency energy (RFe) to the LES resulting in increased LES pressure. In 2000, the FDA approved the Stretta system as treatment for patients diagnosed with GERD. Stretta allows an alternative for treatment in patients who are not willing or able to undergo surgery. The Society of American Gastrointestinal and Endoscopic Surgeons (SAGES) published clinical practice guidelines that endorsed Stretta as an appropriate therapy for treatment of GERD in patients >18, with at least 6 months of symptoms partially or completely responsive to pharmacotherapy and who are unable or unwilling to undergo laparoscopic Nissen fundoplication. There are to date no studies evaluating the use of Stretta in management of patients with GERD symptoms after sleeve gastrectomy.

1.2 Compliance Statement

This study will be conducted in full accordance of all applicable Montefiore Medical Center Research Policies and Procedures and all applicable Federal and state laws and regulations including 45 CFR 46, and the HIPAA Privacy Rule. Any episode of noncompliance will be documented.

The investigators will perform the study in accordance with this protocol, will obtain consentand assent when applicable (unless a waiver is granted), and will report unexpected problems in accordance with The Montefiore Medical Center IRB Policies and Procedures and all federal requirements. Collection, recording, and reporting of data will be accurate and will ensure the privacy, health, and welfare of research subjects during and after the study.

1.3 Relevant literature and Data

Bariatric surgery is an effective long term treatment for morbid obesity. The number of bariatric procedures performed in the United States has increased significantly in the recent years. The American Society for Metabolic and Bariatric Surgery (ASMBS) estimates that in The United Statesin 2013 approximately 179 thousand bariatric caseswere performed. The number of sleeve gastrectomiespreformed in the US has increased from being only 17% of the bariatric cases in 2011 to over 42% in 2013 and continues to increase. This increase in numbers is because SG has proven to be a very safe procedure with excellent weight loss results. There is conflicting data on theeffect of SG on patients with preexisting GERD. Although the pathophysiology is not fully understood, GERD following SG is usually attributed to a decreased lower esophageal sphincter (LES) pressure, disruption of the sling fibers, dissection of the angle of His or elevated intragastric pressure. In cases with severe GERD, patients may have to undergo a revision to RYGB, as this is the only available treatment for refractory GERD after SG.

Studies investigating the incidence of GERD following SG have many limitations and are poorly designed. First, the surgical technique is not standardized. Different techniques can result in various sleeve sizes and can also result in gastric stenosis at the incisura or in a residual large fundus, which can all, affect the incidence of GERD postoperatively. Second, the true incidence of GERD in patients undergoing SG is largely unknown because patients do not routinely undergo preoperatively workup for GERD. Third, many patients develop non-specific gastrointestinal symptoms like regurgitation, bloating and chest pain, which are sometimes attributed to GERD or even hiatal hernia without any confirmation of the diagnosis. The postoperative use of proton pump inhibitors or other antisecretory medications as well as initial healing time followed by relaxation/dilatation of the gastric sleeve a few months following SG can influence symptoms of GERD. Therefore, data regarding the incidence of GERD following SG should be obtained at least 6 months postoperative at which time the majority of weight loss has been achieved, medications stopped and changes have stabilized.

There has been in recent years a large number of endoscopic procedures that have been used as an alternative to the surgical anti-reflux procedures with various degrees of success. The delivery of RFe to the LES by the Stretta device results in increased LES pressure. The Stretta device is FDA approved and has excellent results in the treatment of GERD symptoms in the standard population. The aim of this study is to objectively investigate the effect of RFe to the LES in patients who develop GERD related symptoms after SG. Patients who experience GERD related symptoms 6 months after SG will undergo the Stretta procedure. The data collected from EGD, pHmonitoring in junction with GERD Health-Related Quality of Life (HRQL) questionnaire prior to the Stretta procedure, will be compared with data following the Stretta procedure at 6, 12 and 24 months.

2. Study Objectives

2.1 Primary Objective

The primary objective of this prospective study is to evaluate the treatment success as measured by percent reduction of symptoms. Following the use of radiofrequency energy delivered to the lower esophageal sphincter as a treatment of symptomatic GERD, in patients who have undergone sleeve gastrectomy for morbid obesity. The endpoint of interest is whether patients achieved a 50% reduction in symptoms as measured by RSI and HQRL indices.

2.2 Secondary Objectives

The secondary objectives are:

- To determine the pH findings in patients with symptomatic GERD after SG
- To determine the effects of gastric emptying and its association to GERD in patients after SG
- To follow the long term effect of Stretta in patients with symptomatic GERD after SG

3. Investigational Plan

3.1 General Schema of Study Design

3.1.1 Multicenter prospective study

This is a multicenter prospective study involving ten to fifteen tertiary medical centers. We expect to enroll at least twenty patients per center. Pre-procedure all enrolled patients will undergo a battery of testing in order to ensure that they are an adequate candidate for Stretta. The workup will include:

- pH monitoring(off medication)
- EGD with biopsies
- Barium swallow
- Gastric Emptying study
- RSI and GERD-HQRL
- Manometry, if dysphagia is reported

This will be followed by endoscopic radiofrequency energy delivery utilizing the Stretta system. Patients will be followed and evaluated at 6, 12, and 24 months with RSI and GERD-HRQL scoring as well as interval pH testing. At 6 and 12 months those subjects with initial abnormal pH,Gastric emptying or EGD will repeat pH monitoring,gastric emptying and EGD

3.1.3 Enrollment

Patients may be enrolled prospectively or retrospectively up to 6 months following Stretta procedure.

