3.2 Criteria For Evaluation

3.2.1 Primary Endpoint

• Primary endpoint will be based RSI and HQRL indices and will be a determination of whether the patient achieved at least a 50% reduction in symptoms at the 6 12 and 24 month points as compared to baseline.

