4.3 Pre-procedure Testing

EGD

The upper endoscopy of SG patients with GERD symptoms will be performed under IV sedation per institutional guidelines. Biopsies of any suspicious lesions and of any evidence of esophagitis will be taken. Evidence of esophagitis will be scored by histology and according to LA classification:

Grade A	One or more mucosal breaks < 5 mm in maximal length
Grade B	One or more mucosal breaks > 5mm, but without continuity across mucosal folds
Grade C	Mucosal breaks continuous between > 2 mucosal folds, but involving less than 75% of the esophageal circumference
Grade D	Mucosal breaks involving more than 75% of esophageal circumference

Following upper endoscopy, assuming that there are no contraindications noted, the patient will then undergo a motility and 24 hour pH testing.

pH monitoring

Bravo pH monitoring will be performed off proton-pump inhibitors (PPI) or anti-secretory drugs. Subjects taking any of these medications will be required to discontinue them for at least one week. Subjects who are unable to discontinue their medications will be excluded from the study. At the discretions of each site and pending site availability catheter based pH monitoring can be used.

Barium Swallow

The Barium swallow will be performed per institutional guidelines. Assessment of esophageal motility and any evidence of dilation will be recorded. Subjects who have any evidence of abnormally enlarged sleeve, evidence of twist, or large residual fundus will be excluded from study.

Gastric Emptying Study

The Gastric Emptying study will be performed per institutional guidelines. Assessment of gastric emptying for all patients at 1, 2, 3 and 4 hours, will be documented. Subjects who have severe gastroparesis(over 50% retention at 4 hours) will be excluded from study.

RSI/HQRL

Patients will complete a GERD Health Related Quality of Life questionnaire (HRQL) (Addendum 1) and Reflux Symptom Index (RSI) (Addendum 2) at baseline off medications and following the Stretta procedure at 6,12 and 24 months if patient has required to restart antisecretory medication at any time a new trial to discontinue medication will be attempted and questionnaires shall be completed while off medications for at least 1 week.

Manometry

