Esophageal manometry will be performed in any patients who refer any symptoms that may suggest dysphagia or if contrast study shows evidence of severe dismotility, if positive for motility problems it will exclude subject from study.

5. Study administration

Catheter-based manometry and Bravo pH monitoringStudies

The use of manometry will be at the discretion of the physician if there is any suspicion of motility abnormalities. All subjects will have pH monitoringas baseline prior to Stretta procedure if abnormal it will be repeated at 6 month and 12months. Results will be collected and reviewed by the investigators at each site and reported using confidential password protected files.

As part of the submission and review process the studies will be inspected by the designated investigator and evaluated for:

- 1. Quality of data collected.
- 2. Correct use of the diary information and patient symptoms entries.
- 3. Artifacts will be noted and excluded from the calculation.
- 4. Confirmation of diagnosis regarding the presence or absence of reflux events, and correlation of reflux events with patient symptoms.
- 5. Data will be collected of the following data entries:
 - a. LES length
 - b. LES pressure
 - c. % normal peristalsis
 - d. Total number of reflux events
 - e. Time pH < 4 min
 - f. Total fraction time % pH < 4
 - g. DeMeester Score
 - h. Correlation of symptoms with reflux events

Stretta Procedure

Stretta will be performed while patient is on anti-secretory agents. Subjects will continue taking these medications for four weeks post procedure. After the fourth week they will decrease to half dose for 2 week and then discontinue medication.

Stretta is a safe, non-invasive FDA approved procedure performed endoscopically under moderate sedation or general anesthesia which uses radio frequency (RF) energy applied to the lower esophagus over 14 minutes per a specific FDA approved protocol and as per package instructions for the device. Under endoscopic guidance, a soft tip guide wire will be advanced thru the gastric sleeve and into the duodenum. After removal of the endoscope, the Stretta catheter will be advanced over the wire and the Stretta balloon initially positioned 1 cm above the previously located GE junction. Following the established manufacturer required protocol, the balloon is inflated and needles deployed for each successive treatment level, with RF energy applied under the control of the Stretta version 2 generator.

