6.1 Statistical Methods

Data will be entered on an excel spreadsheet and analyzed with SAS v9.3. Data analysis will be preceded by quality control of our data which will include checks for accuracy, completeness and internal validity. Rates of achievement of 50% reduction of symptoms will be computed and reported with their 95% confidence intervals. Descriptive data analysis will be conducted and all adverse events and overall patient characteristics will be described. The distribution of change in symptom scores will be examined and the decrease in patient symptoms will also be examined and described. If the distribution of this score approximates normality, symptom reduction will be described using mean and standard deviation. Otherwise we will use median and interquartile ranges. Bivariate analysis will be conducted to examine factors associated with achievement of 50% reduction in symptoms. Categorical variables will be analyzed using the Chi-Square's exact test. Continuous variables whose distribution meets normality assumptions will be analyzed with the t-test. Variables whose distribution does not approximate normality will be analyzed using the Wilcoxon rank sum test. While we recognize that the sample size is modest – an exploratory multivariate logistic regression analysis will be conducted to examine factors associated with 50% symptom reduction

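### Section 3.1.3 allows entry up to 6 months after Stretta, so the early course can be known at entry; no baseline condition is stated there and section 6.1 does not mention entry route

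*Combined protocol and SAP*

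**What the plan says.** Section 3.1.3 reads: "Patients may be enrolled prospectively or retrospectively up to 6 months following Stretta procedure". The rest of the plan is written as if entry comes before treatment:

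- Section 2.1 gives the design label: "The primary objective of this prospective study is to evaluate the treatment success".
- Section 3.1.1 requires the work-up: "Pre-procedure all enrolled patients will undergo a battery of testing".
- Section 5 requires baseline pH: "All subjects will have pH monitoringas baseline prior to Stretta procedure".
- Section 4.3 has RSI and GERD-HRQL completed "at baseline off medications and following the Stretta procedure".
- Section 3.2.1 defines success by whether the patient "achieved at least a 50% reduction in symptoms at the 6 12 and 24 month points as compared to baseline".

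On anti-secretory drugs after Stretta, section 5 has them continued for four weeks and adds: "After the fourth week they will decrease to half dose for 2 week and then discontinue medication".

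On analysis, section 6.1 says: "Rates of achievement of 50% reduction of symptoms will be computed and reported with their 95% confidence intervals". It also plans bivariate analyses and an exploratory logistic regression of factors associated with success. Entry route is not named in any of these. Section 6.4 ties the ongoing safety review to the treatment of each patient, not to enrolment.

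**The concern.** In a single-arm study the main result is a proportion among whoever was entered. If the decision to enter a patient can follow sight of how that patient is doing, the proportion depends partly on that decision. A 95% confidence interval describes sampling error only and does not widen for this.

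The 6-month success rate is the most exposed, because the entry window runs up to that assessment. The adverse event counts are exposed too: a peri-procedural complication has already happened, or not, when a late entrant is enrolled. The 1-year rate, on which section 6.2 bases the sample size, is affected only as far as it correlates with the early course.

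Two gaps in wording add to this. Section 3.1.3 does not say that a late entrant must already hold the work-up and baseline scores, and without baseline scores the primary endpoint cannot be computed. Section 6.4 does not say whether a patient treated but not yet entered counts towards the perforation and death limits.

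**Working it through.** **1. What can be known at entry.** Inputs: the 6-month window (3.1.3), about 26 weeks, and the taper in section 5.

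- Off medication from week 4 + 2 = 6.
- Part of the window after that point: (26 − 6)/26 = 20/26 = 77%.

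This is a share of calendar time, not of patients. It assumes that the patient followed the section 5 taper, which is not shown for anyone treated outside the study. No symptom score is scheduled between Stretta and 6 months, so what is visible is the clinical course, not a study measurement. Peri-procedural complications can be known for a late entrant at almost any point. The 6-month result can be known only at the end of the window.

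**2. Is there a conflict over baseline data?** Sections 3.1.1 and 5 apply the work-up and baseline pH to all enrolled patients, before Stretta. Section 4.3 sets the questionnaire baseline off medication. Section 3.1.3 grants no exemption. Read together, a late entrant must already have these data, for example from routine care. That is a consistent reading, but 3.1.3 does not state it.

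**3. The plan's precision figures.** The exact (Clopper-Pearson) interval reproduces section 6.2:

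- 25/50: 0.355 to 0.645, width 0.289 (stated 0.289).
- 35/50: 0.554 to 0.821, width 0.267 (stated 0.267).

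No stated figure is in dispute.

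**4. Precision of an analysis restricted to patients enrolled before the procedure.** The documents do not give the share of late entrants. As an example, assume 40 of the 80 are enrolled before Stretta. The 30% dropout in section 6.2 refers to 24 months.

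- All entrants: 80 × 0.70 = 56 evaluable; exact width at p = 0.5 (28/56) is 0.273.
- Restricted: 40 × 0.70 = 28 evaluable; exact width at p = 0.5 (14/28) is 0.387.
- At 1 year the restricted number lies between 28 and 40; the width at p = 0.5 is then 0.387 to 0.324.

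**The case against.** **The label and the baseline.** Scheduled outcomes fall at 6, 12 and 24 months, at or after the latest permitted entry, so the word prospective can describe how outcomes are collected. The work-up is required of all enrolled patients. This stands: a reader might infer that 3.1.3 contradicts the baseline requirements, or that late entrants will lack baseline data. The documents support neither. What remains is a condition that 3.1.3 leaves unstated.

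**The selection rule.** The text between 3.1.1 and 3.1.3 was not available for this review. A consecutive-patient rule may be there, so its absence cannot be asserted. The silence of 6.1 on entry route does not depend on that text.

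**The size.** A reader might want to say that the success rate is inflated by some number of points. That would need the share of late entrants, the strength of selection and the agreement between early course and later result. The documents give none of them. The direction is open as well: satisfied patients may be easier to enrol, or dissatisfied ones may return more often.

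**The main estimate.** A reader might conclude that patients enrolled before the procedure must become the main analysis. That is a trade-off, not a correction. At p = 0.5, root-mean-square error is √(0.25/n + bias²). For the restricted estimate with n = 28 and no bias it is √(0.25/28) = 0.094. For all entrants with n = 56 it is √(0.25/56 + 0.03²) = 0.073 with an assumed bias of 3 points, and √(0.25/56 + 0.05²) = 0.083 with 5 points. The restricted estimate is better only if the bias exceeds √(0.25/28 − 0.25/56) = 0.067, and nothing in the documents shows a bias that large.

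**Safety counts.** The 6.4 wording is ambiguous. It does not show that events would go uncounted.

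**Conclusion.** The concern holds as a gap in the entry rule and in the reporting. Followed as written, section 3.1.3 permits entry after the early course and any complication are known and, at the end of the window, after the 6-month result. In a study without a control arm, this leaves the 6-month success rate and the adverse event counts open to selection outside the stated interval, and the 1-year rate to a lesser degree. Neither direction nor size can be derived from the documents, and no numerical bias is claimed. The planned interval widths are correct for sampling error.

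The conclusion rests on the plain wording of 3.1.3 and 6.1. It does not assume that late entrants lack baseline data or that sites would select patients deliberately. Confidence is medium, because a selection rule may stand in the text not available here. The point should be fixed: the changes are small, and selection that was not recorded during accrual may not be recoverable later.

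**What to change.** 1. **Section 3.1.3.** Allow post-procedure entry only for patients with a documented pre-procedure work-up and off-medication baseline RSI and GERD-HRQL, entered consecutively. Have each site log all eligible Stretta-treated post-sleeve patients, with entry route, time from Stretta to entry and reason for non-enrolment. If the section before 3.1.3 already holds a selection rule, refer to it here.
2. **Section 6.1.** Report success and adverse event rates by entry route. Pre-specify a sensitivity analysis restricted to patients enrolled before the procedure. Add entry route to the factors examined in the planned bivariate and exploratory logistic analyses.
3. **Section 6.4.** Reconcile the review after each treated patient with 3.1.3 by stating which treated patients it counts.

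The cost is a log at each of the 10 to 15 centres and lower precision in the restricted analysis. In the example of 28 evaluable patients, the exact width at p = 0.5 is 0.387, against 0.289 with 50 or 0.273 with 56. The overall estimate and the target of 80 can stay as they are.

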3.2 Criteria For Evaluation

3.2.1 Primary Endpoint

• Primary endpoint will be based RSI and HQRL indices and will be a determination of whether the patient achieved at least a 50% reduction in symptoms at the 6 12 and 24 month points as compared to baseline.

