6.2 Sample Size and Power

The target number of patients proposed for this protocol is based on our primary objective of estimating the proportion of patients achieving at least a 50% reduction of symptoms from baseline as measured by RSI and HQRL indices 1 year post treatment. Sample size calculations are based on this primary objective. Our target sample size is 80 unless perforation occurs in more than 2 patients or more than one death directly related to Stretta procedure or the accrual is terminated during interim analysis. A sample size of 50 would produce a two-sided 95% confidence interval with a width of 0.289 for a proportion of 0.5 and a width of 0.267 for proportions of 0.7. Taking into consideration that given improvement of symptoms or other factorswe estimate a 30% patientsdropout prior to completing the 24 month follow-upwe will increase target sample size to a total of 80 patients

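### The primary responder rule rests on the symptom score alone and does not say how to classify a patient who has bypass conversion, repeat Stretta or another anti-reflux procedure during follow-up

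*Combined protocol and SAP*

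**What the plan says.** - Section 2.1 sets out to "evaluate the treatment success as measured by percent reduction of symptoms", so the score reduction is itself the definition of success.
- Section 3.2.1 defines the primary endpoint as "whether the patient achieved at least a 50% reduction in symptoms at the 6 12 and 24 month points", relative to baseline. It puts no condition on treatment received after the study procedure.
- Section 6.1 gives the primary analysis: "Rates of achievement of 50% reduction of symptoms will be computed and reported with their 95% confidence intervals". It has no rule for patients re-treated during follow-up and none for missing scores.
- Section 6.2 sizes the study on the proportion reaching the 50% reduction "as measured by RSI and HQRL indices 1 year post treatment".
- Section 1.3 says that in severe cases "patients may have to undergo a revision to RYGB, as this is the only available treatment for refractory GERD after SG". Section 1.1 says "RYGB has proven to be the most effective surgical treatment for GERD in the morbidly obese patient".
- Exclusion 5 in section 3.2.4 (revisional bariatric surgery) concerns history at entry, not surgery after Stretta.
- Section 4.3 addresses restarted antisecretory drugs. A further attempt to stop them is made, and the questionnaires are completed after at least a week off them.
- Section 4.1 records changes in medication at each follow-up visit but does not name procedures performed between visits.

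**The concern.** A patient whose reflux persists or returns after Stretta is the patient most likely to be offered another procedure. If that procedure works, the score falls, and a rule that looks only at the score moves a Stretta failure into the numerator. The reported rate then describes Stretta plus whatever followed it.

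Section 3.1 describes no comparison group, so the responder proportion is the main result and nothing offsets the error. Against a rule that counts such patients as failures, score-only counting can only raise the rate or leave it unchanged. A larger sample would not remove this. There is more time for such procedures to accumulate by 24 months than by 12, and 24 months is the last visit available for the long-term objective in section 2.2.

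The protocol deals with the parallel problem for drugs by asking for scores off medication. A bypass cannot be washed out in that way, and no equivalent rule exists for procedures.

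**Working it through.** **Inputs.** From section 6.2: 50 evaluable patients, two-sided 95% interval, stated widths 0.289 at a proportion of 0.5 and 0.267 at 0.7, 30% dropout before 24 months, target 80. The number of patients having a later reflux procedure is not in the documents. It is assumed below as 0 to 10 among 50 (0% to 20%), all of them scored as responders.

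**Step 1: reproduce the plan's figure.** Section 6.2 states: "A sample size of 50 would produce a two-sided 95% confidence interval with a width of 0.289 for a proportion of 0.5". The exact (Clopper-Pearson) limits for x responders among n are the 0.025 quantile of Beta(x, n−x+1) and the 0.975 quantile of Beta(x+1, n−x).
- 25/50: 0.3553 to 0.6447, width 0.2895.
- 35/50: 0.5539 to 0.8214, width 0.2675.

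Both agree with the stated widths to within 0.0005. The precision calculation is sound and is not in dispute.

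**Step 2: effect of one patient.** Moving one patient from non-responder to responder adds 1/n.
- n=80: 1/80 = 1.25 points.
- n=56 (80 × 0.70, after the planned dropout): 1/56 = 1.8 points.
- n=50: 1/50 = 2.0 points.

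**Step 3: effect of several patients.** Take a reported 35/50 = 70% (95% CI 55.4 to 82.1) and reclassify k re-treated patients as non-responders, keeping all 50 in the denominator.

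| k assumed | Rate after reclassification | Exact 95% CI | Overstatement |
|---|---|---|---|
| 0 | 35/50 = 70% | 55.4 to 82.1 | 0 points |
| 2 | 33/50 = 66% | 51.2 to 78.8 | 4 points |
| 5 | 30/50 = 60% | 45.2 to 73.6 | 10 points |
| 8 | 27/50 = 54% | 39.3 to 68.2 | 16 points |
| 10 | 25/50 = 50% | 35.5 to 64.5 | 20 points |

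From a reported 25/50 = 50%, k=5 gives 20/50 = 40% (26.4 to 54.8), again a 10-point difference.

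**Step 4: if these patients are dropped instead.** Removing the 5 from numerator and denominator gives 30/45 = 66.7%, still above the 60% obtained when they are kept as failures.

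**Step 5: which patients can be miscounted.** Section 3.2.1 lists the three visits without saying whether success is judged at each one or required at all of them.
- *Judged at each visit.* The 1-year proportion in section 6.2 supports this reading. A patient who fails at month 6, is converted at month 8 and has a low score at month 12 counts as a responder at month 12.
- *Required at all three.* That patient has already failed at month 6 and cannot become a responder. Only a patient who responds early, relapses and is converted, with the threshold met at every visit, would be miscounted.

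**The case against.** The strongest reply is that the plan is silent, not wrong. A reader might infer that it directs converted patients to be counted as Stretta successes. It does not: nothing says that they stay in follow-up or that their later scores are used. They might fall within the 30% dropout. That stands as a limit on the claim, but it does not remove the problem. The scoring rule has no exception for them, no missing-data rule is given, and dropping them also raises the rate (step 4).

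Four further objections hold in part.

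- **Drug re-treatment.** A reader might extend the point to patients who restart antisecretory drugs. The off-medication rule in section 4.3 largely covers them, and cessation or reduction of medication is a separate secondary endpoint in section 3.2.2. The gap concerns surgical and endoscopic procedures.
- **Size.** A reader might infer an overstatement of a definite size. The documents give no conversion rate and no response rate after conversion. The section 1.1 statement on bypass arises in choosing between bypass and sleeve. The same section notes that conversion brings added morbidity and cost, which may keep numbers low, and fewer conversions can have occurred by 1 year than by 24 months.
- **Revisions for other reasons.** Treating every revisional operation as a Stretta failure would misclassify a responder revised for a reason unrelated to reflux and would bias the rate downwards. The rule should be limited to procedures for reflux.
- **Unseen material.** The part between sections 3.1.1 and 3.1.3 and the appendices on the visit schedule and follow-up were not available, and a rule could be there. The endpoint and analysis sections, where it would be expected, were available and contain none.

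**Conclusion.** The gap is real for procedures. As written, the endpoint can count a patient who had conversion to bypass, repeat Stretta or another anti-reflux procedure as a Stretta responder, and that error can only favour Stretta. How many patients are exposed depends on the reading of section 3.2.1: the visit-by-visit reading leaves the gap widest, and the all-visits reading confines it to early responders who relapse.

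The per-patient effect (1.25 to 2.0 points) is arithmetic. The 10-point shift for 5 among 50 is an illustration that assumes both the number of patients and that all of them meet the 50% rule after re-treatment. It is not a forecast.

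The point should be fixed, but it does not invalidate the design. The analysis is a descriptive estimate with no hypothesis test and no success threshold, so no stated decision turns on it, and the sample size is unaffected.

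**What to change.** In sections 3.2.1 and 6.1, state that for the primary analysis a patient who has a surgical or endoscopic procedure for reflux before an assessment (conversion to bypass for GERD, repeat Stretta or another anti-reflux procedure) is a non-responder at that assessment and all later ones, whatever the score, and stays in the denominator. Say in the same place whether success is judged at each visit or required at all three.

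Add a follow-up field for the type, date and reason of every procedure between visits. Do not automatically count revisions for reasons unrelated to reflux as failures. Report the number, timing and reasons of these procedures beside the responder rate, and keep the score-only rate as a sensitivity analysis. Settle the rule before outcome data are examined.

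The cost is a short addition to two sections, one extra data field and a headline rate that may be lower. The 50 evaluable and 80 enrolled patients stand. The rule classifies outcomes only and directs no patient's care.
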